- 18. REDCap will send weekly reminders to subjects concerning when to start self-treatment A, when to start self-treatment B. Treatment group A, 'TRE then Fasting', has a low sugar diet and a 10-12 hour eating window. Treatment group B, 'Fasting then TRE', will have an 8 hour eating window with either a 36 or 60 hour water fast once a week.
- 19. FIRST FAST Subjects will be called after they complete the appropriate survey before their first water fast by a medical student volunteer or [name]. They will be informed of what to expect and reminded to take electrolytes. They will be reminded that they can STOP FASTING at any time. They will also be reminded of how to use the symptom flare-up form (via a public link) to talk to a med student and potentially have [name] call them. Per the new **First Fast Call Medical Student Instructions**, the medical student volunteers are expected to talk with subjects within 24 hours of receipt of a First Fast

email notification. Meanwhile, subjects are instructed not to start their first fast until after they have received their Pre-First Fast Call. If the medical student does not reach the subject, they leave a message with their cell phone number. They then must make at least two call attempts by 4 PST the day after the First Fast Call notification was received. All call attempts and their result will be documented in the subject's First Fast Call for m. As a backup, per the crossover emails, if the participant needs to start their first fast but has not been able to talk with a medical student by 7 pm EST, they may call [name]. [name] will check that the subject is indeed correct to initiate their fast at this time. He will then review the Fasting Safety procedures and update the First Fast Call instrument.

- 20. Survey reminders will be sent using the dateDiff function comparing today's date:time to the survey date of each participant's first Baseline Survey. If a subject misses a key survey, then they are considered withdrawn from the study. The first and third baseline surveys, the survey at the end of 4 weeks water fasting and the survey at the end of the relaxed time-restricted eating are considered key surveys.
- 21. If a subject wants to be removed from the study or no longer qualifies from the study, the subject will be removed, but the record will be maintained.

22.

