With successful completion of the 10 week study, participants will be sent a "Participant Completion" email offering a 30-45 min Study Review conference with an investigator. As an attachment, subjects will get a summary of their participation in the study. It will include their weekly Long Covid Symptom Survey scores and subject comments. Also included in the "Participant Completion" email will be language asking the subject to not share their study Long Covid Symptom Survey scores on social media. The letter will also request that subjects not share the study flier on social media - as recruiting for the study must be done only via investigator posts of the flier on social media.

23. If a subject schedules a Study Review conference, at that time, a participant's results, comments, and adherence to the study procedures will be reviewed. The investigator will again remind the subject to not share their study scores and to not share the study flyer on social media.

Safety Procedures

- 23. During water fasts, subjects are asked to drink salt water for electrolytes twice daily. The recipe has Sodium, Potassium and Magnesium in the proper ratios to replace what would normally be obtained from food. This minimizes the risk of refeeding syndrome (which is already a low risk for short water fasts). ½ tsp Morton Lite Salt in 12 ounces of water. In addition, participants are instructed to take a 200 mg Magnesium Glycinate tablet.
- 24. If experiencing severe symptoms, they are to fill out the Symptom Flare-up form via the link in their Participant instructions. Their symptoms will be immediately shared with two 3rd year medical students via an automated REDCap e-mail. The form also provides subjects with the medical student's names and phone numbers. They will try to provide 24-hour support for study subjects. When a medical student identifies a safety concern, they will be referred to [name]. [name] will recommend if the subject should contact 911 emergency immediately and/or be removed from the study. [name] will then report the removal of the subject.

25.

As subjects complete their weekly Symptom Surveys, REDCap notifications will check for self-reported Serious and Concerning Adverse Events.[name], [name] and [name] will be sent all Adverse Event notifications as they are reported. The Investigator or Co-Investigator will create an Adverse Event instrument in REDCap within 24 hours. They will also contact the subject if additional

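### Step 24's severe-symptom alert lists two medical students as its recipients, and the person who advises on 911 or removal joins only on a student's referral

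*Combined protocol and SAP*

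**What the plan says.** Three steps of the protocol bear on this point.

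- **Step 24 (Safety Procedures).** A participant with severe symptoms is to "fill out the Symptom Flare-up form via the link in their Participant instructions". Then: "Their symptoms will be immediately shared with two 3rd year medical students via an automated REDCap e-mail". On direct contact: "The form also provides subjects with the medical student's names and phone numbers". On cover: "They will try to provide 24-hour support for study subjects". Escalation is conditional: "When a medical student identifies a safety concern, they will be referred to [name" (the name is removed from the public copy). That person "will recommend if the subject should contact 911 emergency immediately and/or be removed from the study".
- **Step 19 (Study Procedures).** Before the first fast, participants are reminded that the flare-up form lets them "to talk to a med student and potentially have [name] call them". This is the same order as in step 24: student first, adviser possibly second. For the routine call before the first fast, step 19 also sets a 24-hour expectation, at least two call attempts, documentation, and a backup person to phone if no student has been reached.
- **Step 25 (Safety Procedures).** Adverse event notices go to three named people as events are reported. They are raised when a participant completes the weekly Symptom Survey, not by the flare-up form. An investigator then opens the adverse event record within 24 hours, serious forms are completed within 48 hours of notification, and Concerning events are reviewed on Thursdays.

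**The concern.** The trial is fully remote. It asks for water fasts of up to 60 hours from people with Long COVID, and it excludes anyone who has already fasted for more than 18 hours with the condition. The protocol states that there are no earlier studies of fasting in Long COVID. With so little experience to draw on, prompt escalation of a bad reaction matters.

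On the stated route, deciding whether a flare-up is a safety concern falls first to students whose cover is best effort. By contrast, on the adverse event forms in step 25 even the investigators leave the medical judgment fields to a designated person. A misjudged flare-up, or an alert that neither student sees in time, would leave the person assigned to advise on 911 or removal uninformed through this route. What is at stake is participant safety. No effect on the trial's estimates or conclusions is claimed.

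**Working it through.** The plan gives no figure to reproduce. The check compares the two routes, works out how late the second could be, and asks how much fasting remained.

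**1. The two routes**

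- Flare-up form (step 24): immediate; goes to two students; reaches the adviser only if a student identifies a concern; no response time stated.
- Weekly survey (step 25): goes directly to three named people; prompt once triggered; not triggered until the survey is completed.

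No other recipient of the flare-up e-mail appears in the protocol or SAP. Step 24 does not use the word only; that reading comes from its listing two students and nobody else.

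**2. Delay if the student route fails**

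Inputs: the Brief Summary puts fasts at the beginning of the week and surveys at its end. Assumption: the survey falls on day 7 and is completed.

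Delay = 7 − day of onset.

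- Onset on day 1: 7 − 1 = 6 days. Onset on day 3: 7 − 3 = 4 days.
- Onset on day 4: 7 − 4 = 3 days. Onset on day 6: 7 − 6 = 1 day.

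As a check against the protocol's own description, the time from the end of a fast begun at the start of the week to the end of that week is 7 − 60/24 = 4.5 days for a 60-hour fast and 7 − 36/24 = 5.5 days for a 36-hour fast. Both agree with the 5-day washout in the Brief Summary. The 24-hour, 48-hour and Thursday steps come after notification and are not added to the delay.

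**3. Fasting left when version 3.0 was dated (21 July 2023)**

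Inputs: last recruitment planned for April 2023 (Synopsis, Schedule); duration 10 weeks, or 70 days (step 15).

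- Starting on 30 April 2023: 30 April + 70 days = 9 July 2023, which is 12 days before 21 July.
- The last fasting week begins on day 63 in Arm AB (week 10) and on day 35 in Arm BA (week 6). For it to begin on or after 21 July, the first baseline survey must fall on or after 21 July − 63 days = 19 May 2023 (AB) or 21 July − 35 days = 16 June 2023 (BA).

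Actual recruitment dates are not given. SAP section 2.0 (Study Population) describes 58 participants, in the past tense, as having engaged in all 10 weeks.

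**4. Scale**

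Planned: 96 × 4 = 384 weekly fasts. On the SAP's population: 58 × 4 = 232. Neither is a count of flare-ups. The documents give no flare-up rate and no rate at which students would miss one.

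**The case against.** The strongest objection is that much of the relevant material is not in the file. The flare-up form, Participant instructions, crossover e-mails and contact and consent pages are unavailable and may give a backup number or tell participants to call 911 directly. Names are removed, so the step 19 backup and the step 24 adviser may be the same person, whose number participants may already hold. This stands. A reader might infer that the trial has no backup for flare-ups; the documents do not support that, because they cannot show what the unseen material says.

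Existing safeguards also count. Two students are alerted, so each covers for the other. Participants have the students' numbers and are told they may stop fasting at any time. Their own health care providers are to receive a letter (step 14), and people with diabetes, heart conditions or a past eating disorder are excluded. The SAP says investigators will keep close contact with participants, although it says so under data quality. Nothing makes a participant wait for study advice before calling 911, so it would be wrong to infer that students control access to emergency care.

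The delay of 4 to 6 days depends on several things happening together: an early reaction, a failed student route, no other contact, and a day-7 survey. No probability can be put on that chain, so the figure should not be read as an expected delay or a measured harm.

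Finally, having students triage first is a legitimate design choice. That is accepted, and the fix leaves it in place. What survives is narrower and rests on text that is present: the stated recipient list, the best-effort cover and the referral condition.

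**Conclusion.** The point holds in a limited form. As written, step 24 makes the adviser's involvement depend on a student identifying a safety concern. If that fails, the only other study route the protocol body states is the weekly survey: about 4 to 6 days later for onset on days 1 to 3, and 1 to 3 days later for onset on days 4 to 6. These figures assume a completed survey on day 7.

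The change should be made if any fasting remains or enrolment continues. Approval covers 180 participants, so further enrolment is possible. Otherwise there is little left to protect. A reader might take the 384 planned fasts as the number exposed to this gap, but the SAP's 58 participants give 232, and the planned dates suggest few or none fell after version 3.0. This is not conclusive, because the SAP carries no separate date and actual recruitment dates are not given. Confidence is medium.

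**What to change.** In step 24, add the adviser already named there as a recipient of the existing automated flare-up e-mail. Students remain first-line, and the recommendation on 911 or removal stays with the same person. This takes one added recipient on a REDCap alert and a matching change to the step 24 sentence, with no new staff. The downside is some extra e-mails to that person, in a number the documents do not allow to be estimated.

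Naming a phone contact for use when no student answers is optional wording, since the form or Participant instructions may already give one. If the sponsor adds it, the contact's availability should be confirmed first: the step 19 backup is described only for starting a first fast, and round-the-clock cover is not stated for that person.

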1.0 Study Overview

Introduction. Post-acute sequelae of COVID-19 (PASC), or Long COVID, is composed of a constellation of symptoms that arise after resolution of acute SARS-CoV-2 infection and constitutes an on-going crisis of international public health. Estimates of the incidence of Long COVID vary from between 6-10% in current literature, although this varies depending on definitions and estimates were higher in earlier phases of the pandemic. A majority of those reporting Long COVID are female. COVID-19 is known to directly target activated T cells and to inhibit or disable autophagy. The causes of Long COVID remain under investigation, but evidence suggests that viral persistence, persistent micro-clotting, autoantibodies, reactivation of Epstein-Barr Virus, and energy dysregulation may play a role. No proven treatment currently exists for Long COVID.

Water-only fasting is reported to activate various mechanistic pathways such as autophagy, decrease excessive inflammation, deactivate T cells and protect activated T cells, and generally strengthen the immune system. Various regimens of fasting exist, with the most popular being shorter-term durations, or intermittent fasting, in which caloric intake ceases for 2 days or less. Intermittent fasting regimens include fasting every day for 14-16 consecutive hours (also known as time-restricted eating or TRE), once per week for 24 hours, two days per week on either consecutive or non-consecutive days, and fasting every other day (also called alternate-day fasting). Whether intermittent fasting reduces the severity of acute COVID-19 or PASC/Long COVID is untested but theory suggests that it should directly counteract many of the main adverse effects of COVID-19.

1.1 Study Aims

1.1.5 **Primary aim:** Determine if self-treatment with 23- to 60-hour water fasting once per week in addition to eating in a daily 8-hour TRE window (i.e., daily 16-hour water fasting) and eating a low-sugar diet reduces overall Long COVID severity, as measured by sixty symptoms of Long COVID.

1.2.5 Secondary aims:

- 1.2.1.5 Determine if eating in a 10- to 12-hour TRE window daily (i.e., 12- to 14-hour daily fasting) and eating a low-sugar diet reduces overall Long COVID severity.
- 1.2.2.5 Determine if the self-treatment of 23- or 60-hour water fasting once per week for four weeks (in addition to 8-hour TRE and a low-sugar diet) reduces the severity of twenty-eight common Long COVID symptoms.
- 1.2.3.5 Determine if eating in a 10- to 12-hour window daily and avoiding sugar for four weeks reduces the severity of twenty-eight common COVID symptoms.
- 1.2.4.5 Determine which is more efficacious for reducing severity of Long COVID: a once-weekly 23- to 60-hour water fast with daily substantial 8-hour TRE (16-hour fasting) and a low-sugar diet OR a daily modestly-restricted TRE and low-sugar diet.

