DIET AND FASTING FOR LONG COVID; A CROSSOVER TRIAL

7/21/2023

NCT06214455

Trial Protocol and Statistical Analysis Plan

- Trial Protocol
- Statistical Analysis Plan (page 11)

Clinical trial protocol

SYNOPSIS

TITLE	Diet and Fasting for Long COVID
RESPONSIBILITY	[name]
	Principal Investigator
	Pacific Northwest University - Health Sciences
	College of Medicine, Department of biomedical Sciences
	[name]
	[name]
	Co-Principal Investigator
	Unaffiliated Patient Researcher
	[name]
STUDY CENTER	Pacific Northwest University - Health Sciences
	College of Medicine, Department of Biomedical Sciences
	[name]
PRIMARY OBJECTIVE	Change in Long COVID Symptom Severity Scores and Symptoms during Treatment A (diet, not-fasting) vs Treatment B (diet, fasting).
STUDY DESIGN	Interventional, randomized, all remote, two-arm crossover study, not blinded
STUDY ARMS	Experimental: Arm AB (Diet then Diet and Fasting)
	1. 2 week baseline with a low sugar diet and 10-12 hour eating window
	2. Treatment A: Eat a low sugar diet, 10-12 hour eating window for four weeks

	3. Treatment B: Eat a low sugar diet, 8 hour eating window, 23 to 60 hour fast once a week for four weeks
	Experimental: Arm BA (Diet and Fasting then Diet)
	1. 2 week baseline with a low sugar diet and 10-12 hour eating window
	2. Treatment B: Eat a low sugar diet, 8 hour eating window, 23 to 60 hour fast once a week for four weeks
	3. Treatment A: Eat a low sugar diet, 10-12 hour eating window for four weeks
SAMPLE SIZE	96 Long Covid subjects (approved for 180)
INCLUSION CRITERIA	Adult (18-69 years old)
	Five or more common Long Covid symptoms
	 Free from fever > 100F and known bacterial and parasitic infections
	 Must indicate willingness to limit certain supplements and report all medications.
	 Must indicate willingness to make significant dietary changes - and limit daily eating to an 8 or 10 hour window.
	 Must indicate willingness to attempt 36 hr or 60 hr water fasts each week for 4 weeks.
	Have a valid email address and phone number
	Reside in the United States
	Be able to read and to communicate in English

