This study uses a cross-over design to test a diet change plus a 10-12 hour eating window (Treatment A) compared to a diet change, an 8-hour eating window and one 36-60 hour fast per week (Treatment B) in subjects screened to have a minimum of five long COVID-19 symptoms. Fasting is for food only, but water is available. There is a two-week run-in with symptom surveys at the start (Week 0) and end (Week 2), followed by randomization to either ARM AB or ARM BA (with weekly symptom surveys). Since the water fasts are at the beginning of the week (with symptoms surveyed at the end of the week) there is a 5 day washout and then a cross-over to the other treatment for 4 weeks.

Study Hypothesis

Time-restricted eating and a no added sugars diet decreases Long Covid symptoms and symptoms scores. The addition of weekly water fasts and 8 hr time-restricted eating will result in a greater decrease of Long Covid symptoms than 10-12 hr restricted eating and a no added sugar diet alone over a four-week period.

Study Aims

This study aims to:

- a) Determine if the self-treatment of 36- or 60-hour water fasting once a week for a month reduces overall long COVID severity. If so, to what degree and what is the statistical significance of the results?
- b) Determine if eating in a 10-to-12-hour window daily and avoiding sugar for a month reduces overall long COVID severity. If so, to what degree and what is the statistical significance of the results?
- c) Determine if the self-treatment of 36- or 60-hour water fasting once a week for a month reduces the severity of twenty-eight common long COVID symptoms. If so, to what degree and what is the statistical significance of the results?
- d) Determine if eating in a 10 to 12 hour window daily and avoiding sugar for a month reduces the severity of twenty-eight common COVID symptoms. If so, to what degree and what is the statistical significance of the results?
- e) Determine which is more efficacious: "time-restricted eating, no sugar diet, and a weekly short water fast" OR "time-restricted eating, no sugar diet".

Study Significance and Background:

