2.1 Study Hypotheses

2.1.5 **Primary hypothesis**: The overall Long COVID symptom severity score is lower after 4 weeks of once-per-week 23- to 60-hour water-only fasting [in addition to eating in an 8-

hour daily TRE window (16-hour water fasting) and following a low sugar diet] than after 4 weeks of 10- to 12-hour daily TRE (12- to 14-hour water fasting) and a low-sugar diet.

2.2.5 Secondary hypotheses:

- 2.2.1.5 The overall Long COVID symptom severity score is lower after 1, 2, or 3 weeks of once-per-week water-only fasting (in addition to eating in an 8-hour window daily and a low sugar diet) than after 1, 2, or 3 weeks of 10- to 12-hour daily time-restricted eating and a low-sugar diet.
- 2.2.2.5 The overall Long COVID symptom severity score is lower after the initial 2-week run-in phase of 10- to 12-hour daily TRE and a low-sugar diet reduces Long COVID symptom severity scores.
- 2.2.3.5 The count of Long COVID symptoms is lower after 1, 2, 3, or 4 weeks of onceper-week water-only fasting (in addition to eating in an 8-hour window daily and a low sugar diet) than after 1, 2, 3, or 4 weeks of 10- to 12-hour daily timerestricted eating and a low-sugar diet.

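### The SAP's primary aim names no comparator and has no matching analysis, while its primary hypothesis and the synopsis objective are fasting versus TRE

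*Combined protocol and SAP*

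**What the plan says.** The SAP and the protocol state the main question in several places.

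- **SAP Study Aims 1.1.5 (primary aim).** The aim is to "Determine if self-treatment with 23- to 60-hour water fasting once per week in addition to eating in a daily 8-hour TRE window" and "eating a low-sugar diet reduces overall Long COVID severity, as measured by sixty symptoms of Long COVID". It gives neither a comparator nor a reference time point.
- **SAP Study Aims 1.2.4.5 (a secondary aim).** "Determine which is more efficacious for reducing severity of Long COVID: a once-weekly 23- to 60-hour water fast with daily substantial 8-hour TRE", set against the modest TRE regimen.
- **SAP Study Hypotheses 2.1.5 (primary hypothesis).** "The overall Long COVID symptom severity score is lower after 4 weeks of once-per-week 23- to 60-hour water-only fasting" with its accompanying diet and eating window, "than after 4 weeks of 10- to 12-hour daily TRE (12- to 14-hour water fasting) and a low-sugar diet".
- **Protocol synopsis, primary objective.** "Change in Long COVID Symptom Severity Scores and Symptoms during Treatment A (diet, not-fasting) vs Treatment B (diet, fasting").
- **Protocol Study Aims.** Five aims, a to e, without ranking. Aim a is non-comparative ("Determine if the self-treatment of 36- or 60-hour water fasting once a week for a month reduces overall long COVID severity"). Aim e is the comparison.
- **SAP Trial Endpoints 2.1.5.** Names a composite severity score and a symptom count as primary, without a contrast for either.
- **SAP Analysis Plan 3.3.5 and 3.4.5.** 3.3.5 gives a two-sided paired t-test between treatments. 3.4.5 gives before-after t-tests in all participants (baseline to end of run-in, and baseline to final week) and a repeated measures model between arms. None of these is called primary.

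**The concern.** The primary aim and the primary hypothesis are different questions, and one set of results can answer them in opposite ways. If scores fall equally under fasting and under TRE, severity is reduced under fasting, so aim 1.1.5 is met. The score is then not lower after fasting than after TRE, so hypothesis 2.1.5 fails.

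An equal fall is plausible in this trial. Entry requires at least five symptoms, which invites regression to the mean. Everyone follows the control regimen during the run-in. Treatment is open-label, symptoms are self-reported, and the SAP's Limitations section acknowledges that there is no parallel standard control arm. Only the fasting-versus-TRE contrast is protected by randomisation, and in the list of aims that contrast is secondary.

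**Working it through.** **1. Can aim 1.1.5 be read as comparative?** A reader could take its verb to mean a reduction relative to TRE. Two features of the same list count against that.

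- Aim 1.2.1.5 uses the same verb for the TRE regimen alone. TRE is the control and has nothing below it to be compared with, so there the verb must mean change over time.
- If 1.1.5 were already fasting versus TRE, aim 1.2.4.5 would be redundant.

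The protocol's aims follow the same pattern: each regimen on its own (a to d), then which is better (e).

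**2. Is there an analysis that answers 1.1.5 as written?** The natural one is baseline versus end of fasting. The SAP does not specify it.

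| Test in the SAP | What it measures |
|---|---|
| 3.3.5 paired t-test | Fasting versus TRE |
| 3.4.5 baseline to end of run-in | Change under the control regimen, before any fasting |
| 3.4.5 baseline to final week | Change over 10 weeks, sequences pooled |
| 3.4.5 repeated measures model | Difference between arms over time |

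In the baseline-to-final-week test, 29 of the 58 participants (one half) finish on TRE. It therefore does not isolate the state after fasting.

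**3. Does the sample size show which contrast was meant?** No. SAP Power Calculation gives 40 to 90 per arm without alpha, power, effect size or SD, so the figure cannot be reproduced. At an assumed two-sided alpha of 0.05 and 80% power, it fits a parallel comparison with effect (1.960 + 0.842) × √(2/n): 0.63 SD at n = 40 and 0.42 SD at n = 90. It fits equally well a paired analysis of 80 to 180 people with standardised difference 2.802/√N: 0.31 to 0.21.

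**4. Illustration of what is at stake.** This models a baseline-versus-end-of-fasting test that is not in the SAP. n = 58 comes from SAP Study Population. The rest is assumed: two-sided alpha 0.05, the same fall d at the end of both treatments, no treatment difference, and within-person correlation r.

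- SD of change = √(2(1 − r)), in units of the score's SD
- Noncentrality = d × √58 / √(2(1 − r))
- Critical value t(57) = 2.002

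| r | SD of change | Noncentrality, d = 0.2 / 0.3 | Significant fall, d = 0.2 / 0.3 |
|---|---|---|---|
| 0.3 | 1.183 | 1.29 / 1.93 | 24% / 48% |
| 0.5 | 1.000 | 1.52 / 2.28 | 32% / 61% |
| 0.7 | 0.775 | 1.97 / 2.95 | 49% / 83% |

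In the fasting-versus-TRE comparison the shared fall cancels. The two-sided 5% error splits evenly, so fasting is falsely declared better in 2.5% of trials. A simulation of 20,000 trials per scenario at r = 0.5 and 0.7 gave 2.3% to 2.7%.

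**The case against.** The strongest reply is that the plan as a whole points to the comparison. The synopsis primary objective is A versus B, the protocol's hypothesis expects a larger fall with fasting, the SAP calls TRE the active control, its primary hypothesis is comparative, and 3.3.5 supplies a paired between-treatment test. On this view one loosely worded aim is the outlier.

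Most of that stands. It shows what was probably intended, and it makes the repair small. It does not remove the contradiction, because the sentence labelled primary aim still asks another question and no analysis is named as primary to settle the matter.

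Four stronger readings are tempting, and the documents do not support them.

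- *The SAP plans to claim efficacy from a before-after fall under fasting.* It specifies no such test and announces no such claim, so the percentages above are not the error rate of any planned analysis.
- *The comparison is ranked lowest because it comes last among the secondary aims.* The SAP gives no order of importance among them.
- *The protocol's aims must also change.* They are unranked, and the synopsis objective is already comparative.
- *The size of the risk is known.* The documents give no expected fall and no correlation. If the week-2 survey were taken as the reference, some regression to the mean and run-in response would already be absorbed.

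**Conclusion.** The point holds as an internal contradiction within the SAP, and between the SAP's primary aim and the synopsis objective: the question labelled primary is non-comparative, lacks a matching analysis, and can be met when the primary hypothesis fails. This conclusion rests on the wording alone.

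The illustrative range of 24% to 83%, against about 2.5%, rests on the assumed shared fall and correlations and shows direction only. The change is one the sponsor should make. It does not call the design or the data collection into question.

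**What to change.** Change the SAP wording only.

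1. Make the primary aim the fasting-versus-TRE contrast in the composite severity score at the end of week 4 of each period, matching Study Hypotheses 2.1.5 and the synopsis.
2. Name one within-participant, between-treatment analysis as primary, so that the paired test in 3.3.5 and the model in 3.4.5 do not compete.
3. Move the present 1.1.5 to a descriptive secondary aim.
4. State that any claim of efficacy for fasting rests on the primary contrast.
5. SAP Study Population describes participation in the past tense. Date the change, therefore, and justify it by hypothesis 2.1.5 and the synopsis objective, both of which already stand in the documents.

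No new data, visits or participants are needed. The cost is that a fall from baseline under fasting can no longer be reported as the primary result.
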